**Abstract:** Varenicline is considered to be a first-line tobacco cessation treatment. Previous studies have evaluated the impact of the combination of varenicline and nicotine patches (versus varenicline alone) on smoking cessation, though findings have been equivocal. **No studies to date have evaluated the combination of varenicline and oral nicotine replacement therapy** (NRT; i.e., nicotine lozenges or gum). Nicotine lozenges and gum can provide acute relief during cravings and high risk situations, which offers individuals the flexibility to deliver nicotine when they need it most (in contrast with the continuous and passive delivery of nicotine offered via the patch). Prospective clinical trials are needed in real-world settings to determine whether the combination of varenicline and oral nicotine replacement therapy (i.e., lozenges, gum) is superior to varenicline alone for smoking cessation. The proposed *pilot* randomized trial would enroll 100 participants over 1 year ( $\approx$ 8 participants per month) utilizing a 2x2 factorial design. Twelve weeks of a pharmacological intervention [varenicline + oral NRT (VAR+N) vs. varenicline alone (VAR)] will be crossed with automated medication reminders (reminder messages vs. no reminder messages). All participants will receive an adapted version of the standard counseling offered through the Tobacco Treatment Research Program (TTRP). The primary outcomes will be biochemically-verified smoking cessation at 12 and 26 weeks following a scheduled quit attempt (1 week after enrollment). Smartphone-based ecological momentary assessment (EMA) will be employed to measure withdrawal symptoms, medication adherence, side effects, and adverse events using the Insight™ platform developed by the Stephenson Cancer Center (SCC) mHealth Shared Resource. This pilot study will provide information regarding the feasibility, acceptability, and preliminary efficacy of combination varenicline and oral NRT for smoking cessation, which will support an NIH funding application

for a larger, adequately powered study.

### **Specific Aims:**

**Aim 1:** To determine whether the combination of varenicline and oral NRT (gum or lozenges based on participant preference) increases the likelihood of biochemical-verified smoking cessation relative to varenicline alone at 12 and 26 weeks following a scheduled quit attempt. *It is hypothesized that there will be a trend towards higher cessation rates in the VAR+N compared with the VAR group, with a p-value of ≤ 0.2 supporting further investigation in a larger trial.*

**Aim 2:** To determine the effect of medication reminders on pharmacotherapy adherence and cessation. Participants will be randomly assigned to receive either reminder messages or no reminder messages to take their varenicline as prescribed each day. In addition, those assigned to VAR+N with medication reminders will receive smartphone reminder prompts to use oral NRT at regular intervals. *It is hypothesized that those who are randomized to medication reminders will be more adherent to the medication regimen and more likely to quit smoking than those who do not receive reminders.*

**Aim 3:** To characterize and compare the course of withdrawal symptoms and side effects within the VAR+N and VAR groups measured in real time via EMA, and to determine their influence on the likelihood of cessation. *It is hypothesized that those in the VAR+N group, who are using two pharmacotherapies to address nicotine dependence, may experience less severe withdrawal symptoms than those in the VAR group. However, those in the VAR+N group may also report more medication side effects because two pharmacotherapies are employed. It is expected that withdrawal symptom severity and the presence and severity of medication side effects may mediate the relations between treatment type and cessation outcomes.*

### **A. Background and Significance**

Smoking is the leading preventable cause of death and disease in the United States resulting in over 480,000 premature deaths each year. Although the prevalence of smoking has declined over the past 5 decades, approximately 15.1% of adults continue to smoke in the U.S. Nearly 70% of smokers report that they want to quit smoking, and 55% of all smokers try to quit each year, but only 20% of smokers report that they are planning to quit within the next 30 days. Effective pharmacotherapies to aid cessation are available, and the combination of behavioral support with pharmacotherapy provides optimal cessation outcomes. Most recently, research has focused on evaluating combination pharmacotherapies in an effort to refine current evidence-based treatment approaches. Varenicline alone is currently considered a first-line tobacco cessation treatment. A few studies have evaluated the combination of varenicline and nicotine patches (versus varenicline alone), though the findings have been equivocal. No studies to date have evaluated the combination of varenicline and oral NRT (i.e., nicotine lozenges or gum). Nicotine lozenges and gum can provide acute relief during cravings and high risk situations, which offers individuals the flexibility to deliver nicotine when they need it most, in contrast with the continuous and passive delivery of nicotine offered via the patch. Little is known about the utility of using smartphone apps to provide automated medication reminders. Notably, in clinical trials of combination bupropion and nicotine gum, participants' use of the gum was infrequent, making it difficult to determine whether there might be an added benefit of oral NRT beyond the impact of bupropion alone. Plausibly, scheduled medication reminders might increase adherence to both varenicline and oral NRT. Prospective clinical trials are needed in real-world settings to determine whether the combination of varenicline and oral NRT is superior to varenicline alone, and to evaluate the impact of medication reminders on varenicline and oral NRT adherence.

## **B. Preliminary Studies/Study Team**

Tobacco Treatment Research Program (TTRP). The TTRP led by **[name]** and located at the University of Oklahoma Health Science Center (OUHSC), offers free tobacco cessation treatment to adults from campus or the community who would like to quit using tobacco. The proposed study would take place within the context of the TTRP. Individuals are linked with the TTRP via the electronic medical record and 1-click referrals from clinical departments at the OUHSC or SCC; or from the community by phone [[name]], email ([[contact]](mailto:[contact])), or fax referrals. Treatment includes counseling with a Tobacco Treatment Specialist either in-person or over the telephone and pharmacological treatment. Participants pick up their prescribed medication from the Family Medicine Center (FMC) pharmacy on campus, and the cost of the medication is charged to the TTRP. The TTRP is an Institutional Review Board (IRB)-approved observational research study (OUHSC protocol #6951) where participants complete relevant questionnaires via tablet computers as they receive tobacco dependence treatment. Participants are followed for 27 weeks and compensated for providing smoking status information at key visits (including biochemical verification). Appointments are the TTRP are scheduled by a Tobacco Treatment Navigator, who also manages appointments with counselors for individual treatment. An appointment letter with directions to the TTRP and a map is mailed or emailed to participants after they are scheduled for their first appointment. Participants are reminded of all future appointments via telephone, mail, email, and/or text. Participants with transportation difficulties living in the Oklahoma City metro area may be scheduled for pick-up and drop-off for key visits with SendaRide (<https://sendaride.com>) through their secure dashboard. The TTRP also serves as a recruitment resource for ongoing research studies, and offers a strong resource and structure through which to facilitate the delivery of both empirically-supported and experimental treatments.

Since inception in Oct. 2016, the TTRP has enrolled  $\approx$  500 participants into standard treatment or clinical trials. Enrollment numbers will continue to increase as new OUHSC clinical departments are linked via the electronic medical record, as evidenced by the  $\approx$  300 participants enrolled in the TTRP over the past 12 months. In addition, advertising will be employed to increase enrollment specifically in the proposed research study. TTRP participants are primarily White (55.4%), Black (27.7%), and American Indian (5.6%), and the majority are female (62.1%). Participants report smoking an average of 17.0 ( $SD=9.7$ ) cigarettes per day prior to quitting, for an average of 29.7 ( $SD=13.1$ ) years. Participants are socioeconomically disadvantaged with 21.1% reporting less than a high school education, 44.1% reporting an annual household income of  $<$  \$20,000, and 54.4% reporting that they are uninsured or receiving Medicaid benefits.

Study Investigators. Overall, the study team has an impressive track record of tobacco-related research, and the investigators have varied and complementary expertise, with significant strengths in tobacco cessation intervention and mobile health research. **[name]** is an Associate Professor in the Department of Family and Preventive Medicine in the University of Oklahoma College of Medicine. Her research focuses largely on tobacco cessation intervention among socioeconomically disadvantaged adults, and she is currently conducting two NIH-funded studies within the TTRP that focus on using small financial incentives as an adjunct to standard treatment to improve smoking cessation rates (both studies utilize smartphone-based EMA). **[name]** is an Assistant Professor at the School of Public Health Austin and, and her research interests include the use of technology for health promotion, tobacco prevention and cessation, EMA, and the role of social media in tobacco marketing and health communication. **[name]** is an Associate Professor in the Department of Family and Preventive Medicine in the University of Oklahoma College of

### **C. Research Design and Methods**

**Study Design.** The study will utilize a **2x2 factorial design** in which participants are randomized to pharmacological treatment (VAR+N or VAR) and medication reminders (reminders or no reminders) at baseline (see Table 1). All participants will receive 12 weeks of varenicline after the standard 1-week titration period, with half of participants additionally receiving oral NRT (gum or lozenges, based on participant preference). Those assigned to VAR+N with medication reminders will receive smartphone prompts at scheduled intervals (during waking hours) with a reminder to use oral NRT regularly and as directed. The primary study outcomes will be carbon monoxide (CO)-confirmed 7-day point prevalence abstinence at 12 and 26 weeks post-quit date.

**Table 1. 2 x 2 Factorial Design**

Medication Reminders (Reminders vs. No Reminders)	Pharmacological Intervention (VAR+N or VAR)	
	VAR+N + Reminders	VAR + Reminders
	VAR+N + No Reminders	VAR + No Reminders

## **Study Procedures.**

Recruitment and Screening (Telephone). Adults who are referred to the OTRC Tobacco Treatment Research Program (TTRP), those who respond to study advertisements, and those who have previously enrolled in treatment at the TTRP but remain non-abstinent six months after enrollment will be eligible to be screened for this study (this will allow us to help participants who have failed to quit smoking after receiving treatment). Research staff will contact individuals who may be eligible for this study. Those who are interested in participating will complete a phone- or web-based REDCap screener. Those who meet the initial study inclusion criteria will be scheduled to complete a baseline visit where final screening for study inclusion criteria will be conducted.

Informed Consent/Screening. Informed consent will be obtained from all participants either in-person at the TTRP or remotely using REDCaps electronic signature feature. Individuals will be included in the study if they: 1) are  $\geq$  18 years of age, 2) demonstrate  $>$  6th grade English literacy level, 3) agree to install the study smartphone application onto their personal phone (or agree to carry a study-provided phone with the app), 4) agree to complete phone-based or in-person surveys through 26 weeks post-quit date, 5) currently smoke  $\geq$  5 cigarettes per day, 6) are willing to initiate a quit attempt 7 days after the baseline visit (enrollment), 7) are willing to use nicotine gum/lozenges, 8) are eligible to receive Chantix after a consult with the study physician. Individuals will be excluded from the study if they 1) have a history of seizures, 2) have had an allergic reaction to varenicline, 3) report current suicidality (screen with the MINI Suicidal Scale), or 4) are pregnant, planning to become pregnant, or currently breastfeeding. Please note that the smartphone application for this pilot study is only available in English.

Remote Enrollment. Remote baseline appointments will take place in 2-parts and participants will required to download a video conferencing smartphone app and/or provide photo identification. Participants will be excluded from the study if they cannot download a video conferencing smartphone app and/or provide photo identification. Part 1 will follow same procedure as an in-person visit (informed consent/screening, randomization, questionnaires, and counseling). At the end of part 1, the participant will be mailed Varenicline and if applicable any additional materials (smartphone, Bedfont iCO smokerlyzer, oral NRT). Part 2 will take place once the participant receives the Varenicline and additional materials. During part 2, the participant will be provided with Varenicline instructions and assisted with Insight™ smartphone application set up. The participant will receive the baseline compensation once they complete part 2.

Study Timeline. Enrolled Participants will be followed for a total of 27 weeks. For an overview of study participation, please see figure 1.

Randomization. At the conclusion of the first visit, participants will be randomized to one of the four cells within the 2x2 factorial design (see Table 1): pharmacological treatment (VAR+N vs. VAR) and medication reminders (VAR+N+reminders vs. VAR+reminders only) at the baseline visit. Adaptive randomization will be used to assign participants to groups based upon race, sex, cigarettes smoked per day, and education.

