**Varenicline.** All participants will be evaluated by the study physician, and prescribed varenicline (if eligible). Individuals with a history of seizures, allergic reaction to varenicline, endorse current suicidality, and/or those who are pregnant, planning to become pregnant, or breastfeeding will be excluded from the proposed study. As a precaution, individuals who report current cardiovascular disease will require clearance from the study physician or their personal physician to use varenicline. Notably, recent research has indicated that neither varenicline nor NRT increases the risk of serious cardiovascular events. In December 2016, the FDA lifted the boxed warning for varenicline after findings were published from a large clinical trial showing that the risk of neuropsychiatric adverse events associated with varenicline did not differ from the nicotine patch or placebo, and that varenicline was more effective for smoking cessation than the nicotine patch, bupropion, and placebo (the nicotine patch and bupropion were more effective than placebo). As a precaution, female participants will be advised to avoid pregnancy while taking varenicline and to discontinue the medication should they become pregnant. However, the findings of observational research suggests that taking varenicline does not appear to be harmful during pregnancy. During the first (pre-quit) week of the study, participants will continue smoking and begin taking varenicline. Doses are titrated during the first week of medication (days 1-3: 0.5 mg once daily; days 4-7: 0.5 mg twice daily).

**Oral NRT.** Participants randomized to a VAR+N group will be provided with a supply of 2mg/4mg nicotine lozenges or 2mg/4mg gum (depending on participant preference) and instructed to use a piece as directed after they quit smoking, especially when they have the urge to smoke. Participants will be instructed to chew a piece of gum as follows:

Baseline: every 1-2 hours (12-24 per day)

4-Weeks Post-Quit: every 1-2 hours (12-24 per day), and to begin reducing to at least every 2-4 hours (6-12 per day)

8-Weeks Post-Quit: every 2-4 hours (6-12 per day), and to begin reducing to at least every 4-8 hours (3-6 per day)

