### **Study Measures.**

Screening Measures (online or over the phone). Screening data will be collected using the secure web-based REDCap platform, which provides an intuitive user interface that streamlines project development and improves data entry through real-time validation rules. The initial online screening will include assessment of demographics, smoking history, readiness to quit, and other eligibility criteria.

Traditional Questionnaire Measures. Questionnaire data, including measures of tobacco/health history, sociodemographic characteristics, nicotine dependence, withdrawal symptom severity, depression, perceived stress, mental health, beliefs about medications, medication adherence, and self-efficacy will be collected via REDcap on tablet computers. The amount of time needed for participants to complete the computer-administered questionnaires varies by study visit. It is estimated that the longest visit (baseline) will require one hour to complete. We have found that even individuals with no experience using computers have had few problems completing study assessments. The questionnaire appendix will come from the TTRP IRB 6951.

Biological/Anthropometric Measures. Expired CO levels will be measured at each visit either in-person using the portable Vitalograph ecolyzer or remotely using the Bedfont iCO smokerlyzer which will interface the Insight™ smartphone application. Please note that the Insight™ smartphone application has integrated automated and secure (i.e., encrypted) facial recognition software to ensure that only the participant provides a CO breath sample. Self-reported abstinence from smoking will be verified with a CO level of ≤ 6 ppm at all subsequent post-quit visits. Body Mass Index (BMI) will be calculated (kg/m^2) based on height and weight measurements collected at the baseline visit.

**Ecological Momentary Assessment (EMA).** EMA can accurately measure phenomena in real-time, natural settings. EMA items will identify fluctuations in key variables that predict study outcomes with less bias than traditional in-person assessments.

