#### **D. Statistical Methods**

All questionnaires will be scored using methodology described in the published literature. Sociodemographic information will be summarized using frequencies with associated percentages (categorical/binary outcomes) or means with standard deviations (continuous outcomes). The 2x2 factorial design will be evaluated using logistic regression models, where

smoking status (12 or 26 weeks post-quit date) is included as the dependent variable. The dichotomous variables, medication type (NVAR vs. VAR) and message reminder type (medication reminders vs. no reminders), will be included as independent variables, as well as the interaction term. Sociodemographic covariates and nicotine dependence will be included in the model as covariates. Generalized Linear Mixed Models (GLMM) will be used to examine the influence of EMA variables that are measured repeatedly and are therefore correlated within subjects. The PROCESS macro for SPSS/SAS (described in Hayes, 2013 and available online) will be used to conduct mediation analyses with the goal of identifying variables (e.g., withdrawal symptom severity) that mediate the relation between treatment condition and smoking cessation outcomes. This method uses an ordinary least squares path analytic framework to estimate direct and indirect effects in single and multiple mediation models, and bootstrapping methods are incorporated to generate confidence intervals. The data collected in the proposed study will provide preliminary information for future external funding applications.

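### Section C gives two positions for randomization within the baseline visit; if the listed order is followed, self-reported baseline questionnaires, including nicotine dependence, could be answered with the arm known.

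*Combined protocol and SAP*

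**What the plan says.** Three places in Section C time the randomization.

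- **Study Design** says only that participants are randomized to treatment and to "medication reminders (reminders or no reminders) at baseline". This does not fix the order within the visit.
- **Remote Enrollment** says Part 1 follows the in-person procedure and lists it as "informed consent/screening, randomization, questionnaires, and counseling".
- **Randomization** says: "At the conclusion of the first visit, participants will be randomized to one of the four cells".

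On the use of the baseline data, Section D states: "Sociodemographic covariates and nicotine dependence will be included in the model as covariates". Study Measures gives the source as self-report: "Questionnaire data, including measures of tobacco/health history, sociodemographic characteristics, nicotine dependence". The same sentence goes on to withdrawal, depression, stress, beliefs about medications, adherence and self-efficacy.

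On whether the arm is apparent, the Oral NRT paragraph says: "Participants randomized to a VAR+N group will be provided with a supply of 2mg/4mg nicotine lozenges or 2mg/4mg gum". No placebo gum or lozenge is described for the varenicline-alone arms, and no blinding is described anywhere.

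**The concern.** A covariate earns its place in a randomized comparison by being fixed before allocation. If a self-report scale is completed after the participant has learned the arm, the answer can depend on that knowledge. Adjusting for it can then remove or add part of the treatment contrast. Randomization does not protect against this, and it cannot be repaired once the data are collected.

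In this trial an allocation tells the participant whether they will have one medication or two, and whether they will be reminded to take it. Scales on medication beliefs and self-efficacy are an obvious place for that news to leave a mark.

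Because the Part 1 list claims to describe the in-person visit too, the ambiguity reaches every participant. Staff who follow one paragraph and staff who follow the other would produce baseline data of two kinds under one label.

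**Working it through.** The documents state no figure on this point, so the check is mainly a comparison of texts.

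**1. Can both statements be true?**

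| Source (Section C) | Questionnaires relative to allocation |
|---|---|
| Remote Enrollment, Part 1 list | after, if the list is chronological |
| Randomization paragraph | before, if the questionnaires belong to the visit |
| Study Design | not stated |

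The list has no numbering and no word such as 'then', so it could be an inventory. It reads as a workflow, however: consent and screening come first, and the sentences that follow run on in time through the end of Part 1 and into Part 2. On that reading the two paragraphs conflict.

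**2. Does the mailing step settle it?** No. Oral NRT is mailed at the end of Part 1 where applicable, so the arm must be known by then. That fits either order within Part 1.

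**3. Would the arm be known?** Only the VAR+N groups receive gum or lozenges, and only the reminder groups receive reminders. With no placebo or blinding described, the arm is known once disclosed. The documents do not use the term open-label; this is an inference from what they describe. Nor do they say when the allocation is disclosed.

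**4. Which model covariates are exposed?**

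- Demographics and smoking history are assessed at the online or telephone screener (Study Measures, Screening Measures).
- Race, sex, cigarettes per day and education drive the adaptive randomization, so they must be known before any allocation.
- Nicotine dependence is listed with the questionnaire measures and is not named among the screener items. It is the main exposed covariate.
- The documents do not say whether the sociodemographic covariates in the model come from the screener or from the baseline questionnaire.

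**5. How large could the effect be?** This is an illustration on assumed values only. Suppose knowledge of the arm shifts a covariate by δ SD between groups, and the covariate carries a log odds γ per SD. The adjusted log odds ratio is then off by about −γδ.

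- Assume γ = 0.5 and δ = 0.1 to 0.3: 0.5 × 0.1 = 0.05 and 0.5 × 0.3 = 0.15. As factors on the odds ratio, exp(−0.05) = 0.95 and exp(−0.15) = 0.86. The direction reverses if δ has the other sign.
- For scale, 100 participants give about 50 per medication arm. With abstinence p in both arms, the SE of the unadjusted log odds ratio is √[2 / (50 × p(1 − p))].
- At an assumed p = 0.2: √(2/8) = 0.50. At p = 0.4: √(2/12) = 0.41.
- The ratio of bias to SE runs from 0.05/0.50 = 0.10 to 0.15/0.41 = 0.37.

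None of γ, δ or p comes from the documents, and δ for nicotine dependence could be close to zero.

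**The case against.** The strongest reply is that the parenthetical merely names the components of Part 1. The one explicit statement of timing within the visit stands under the heading Randomization, and it already puts allocation at the end. Figure 1, to which the text refers for an overview, could not be seen and may show the order. This stands as a caution: the documents do not show that questionnaires are in fact answered after allocation. It does not remove the conflict, because the list invites the opposite reading and nothing readable says that allocation waits for the questionnaires.

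Second, the covariates are largely protected. The adaptive factors and the screener items are settled beforehand, and the reference cited for nicotine dependence concerns, by its title, a heaviness of smoking index. That is a measure of smoking behavior, which news of the arm may barely move. This stands, and it is why the exposure is narrow.

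A reader might infer three stronger things, which the documents do not support.

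- **That withdrawal, self-efficacy and medication beliefs are covariates in the primary model.** Section D names only sociodemographic covariates and nicotine dependence.
- **That Aim 3 loses its baseline.** Aim 3 rests on EMA. EMA runs over the 13 weeks on medication, and remote participants set up the app in Part 2, so those data follow allocation under either reading. Neither Aim 3 nor Section D says that baseline questionnaire scores enter that analysis.
- **That a first counseling session with the arm known is a fault.** Counseling continues through 4 weeks post-quit, when the arm is known in any case.

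**Conclusion.** The point holds as an inconsistency within Section C that should be reconciled. On one natural reading it lets self-report baseline scales be completed with the arm known. In the stated primary model the exposure is mainly nicotine dependence. The subjective scales are at risk only as descriptors of the groups at baseline, or in any later adjustment for them.

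The conclusion rests on two readings: that the Part 1 list is in time order, and that the arm is evident once disclosed. If the list is only an inventory, what remains is unclear wording.

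It would go too far to conclude that the primary treatment effect is biased, or that the odds ratio is off by a known percentage. The documents supply no value from which to derive a bias. On the assumed values above it is a fraction of one standard error, in a pilot whose threshold for further study is p ≤ 0.2. CO-verified abstinence does not depend on the order of the questionnaires. The case for acting is that the protection is nearly free and cannot be added after the data are collected.

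**What to change.** Reconcile the two paragraphs of Section C.

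- In Remote Enrollment, list the questionnaires before randomization, for example: consent and screening, questionnaires, randomization, counseling.
- Add one sentence covering in-person and remote visits: the allocation is generated and disclosed only after all baseline questionnaires are complete.
- If counseling stays after randomization, adjust the Randomization paragraph so that it ties allocation to completion of the questionnaires and no longer to the close of the visit. Counseling may stay or move; its position makes no difference to the covariates.
- In Section D, say which source, screener or baseline questionnaire, supplies each sociodemographic covariate. If any participants were enrolled under the other order, report this and prefer screener values for adjustment where they exist.

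The cost is a line or two of protocol text and a check, for instance in REDCap, that the questionnaires are complete before an allocation is requested. No visits, staff or sample size change, and materials can still be mailed at the end of Part 1.
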